³ If there is evidence of a prolonged QTcF interval at screening from the initial (single) administration, then the ECG will be repeated twice, and the mean of the 3 screening administrations will be used to determine whether or not the participant is suitable for inclusion in the study.

immunodeficiency virus [HIV]); renal disease; acquired immune deficiency syndrome; and unstable psychiatric or other neurologic disorders) and metastatic cancer.

For serious kidney and liver illnesses see also exclusion criterion 12 (laboratory test abnormalities).

6. Known intracranial neoplasms, vascular malformations, history of cerebrovascular accident, or intracranial hemorrhage.
7. Female participants who are pregnant, planning to become pregnant or breastfeeding.
8. Medications that prolong QT interval, taken within 4 weeks of the Baseline visit (note, Amiodarone is not allowed within 6 weeks of the Baseline visit) or at any timepoint during the study, including non-allowed antipsychotic medications, tricyclic antidepressants, and/or Class I antiarrhythmics.
9. Use of pridopidine within 12 months before the Baseline visit.
10. Treatment with any investigational product within 6 weeks or 5 half-lives (whichever is longer) before the Screening visit or a plan to participate in another clinical study that assesses any investigational product during the study.
11. Gene therapy at any time.
12. Prior participation in studies with tominersen at any time.
13. Laboratory values that fall outside of the central laboratory's reference range at Screening and are considered clinically significantly abnormal by the Investigator, and affect the participant's suitability to participate in the study or put the participant at risk if he/she enters the study in the Investigator's opinion⁴.
14. Have any of the following laboratory test abnormalities at Screening:
 - a. Creatinine clearance (CrCl) <30 mL/min at Screening, calculated using the Cockcroft-Gault equation: $(140 - \text{age}) \times \text{mass (kg)} \times [0.85 \text{ if female}] / 72 \times \text{serum creatinine (mg/dL)}$ ⁵
 - b. Aspartate aminotransferase (AST) $\geq 2.5 \times$ upper limit of normal (ULN)
 - c. Alanine aminotransferase (ALT) $\geq 2.5 \times$ ULN
 - d. Gamma glutamyl transferase (GGT) $\geq 3.0 \times$ ULN

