- f. After completing the Main Study EoS visit, eligible participants will have the option to continue for an Open-label Extension.
- g. When a participant discontinues study drug but continues to be followed in the study, they should first do ET visit and then continue with the follow-up off study treatment as scheduled.
- h. Visit window can be expanded any post Week 4 (V3) in-clinic visit window to ± 28 days; this applies to V4-8). The expansion of the in-clinic visit window is only in case of a global pandemic.
- i. To be done once, as early as Main Study Week 58, or at V7 (Main Study Week 65)/Main Study Week 72 (depending on when the participant is anticipated to transition to OLE).
- j. Inclusion/exclusion criteria should be met before Baseline visit.
- k. Safety laboratories should not be collected for participants who are off drug and remain in the study, unless there are abnormalities requiring follow-up.
- l. Serum pregnancy test will be performed at Screening. At Baseline visit, urine pregnancy test will be performed before first dose. Both test results must be known before first dosing. Urine pregnancy test will be performed at subsequent timepoints. An indeterminate or positive reading for the urine pregnancy test should be followed-up by a serum pregnancy test and the participant should be referred to a gynecologist if required. During the Treatment period, urine pregnancy tests will be performed monthly. Refer to Appendix 4 Section 10.4.
- m. Single ECG to assess eligibility.
- n. Baseline pre-dose assessment will include triplicate ECG administrations.
- o. Single ECG 1-2 hours post-dose.
- p. Single ECG pre-dose.
- q. Only for participants not continuing to Open-label Extension (single ECG). Participants continuing to OLE, will have triplicate ECG (pre-dose) at V8.
- r. Vital signs (body temperature, systolic and diastolic blood pressure, and heart rate) will be measured in a supine position after 5 minutes rest; thereafter, blood pressure should be measured again after standing for 2 minutes.
- s. For training purposes only.
- t. This information will be collected as part of the concomitant medication inquiry.
- u. Blood samples for plasma concentration of study drug will be collected 1-2 hours **after** dosing and **after** the ECG. PK samples should not be collected from participants who are off drug and remain in the study.
- v. Always collect blood after ECG is administered (not before).

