5.3. Exclusion Criteria – Main Study

Participants are excluded from the study if any of the following criteria apply:

Medical Conditions

1. Prolonged QTcF interval (defined as a QTcF interval of >450 ms for male and >470 ms for female) at Screening⁸.
2. Clinically significant heart disease within 12 weeks before randomization, defined as follows:
 - a. Participants with clinically significant heart disease, a clinically significant history of arrhythmia, symptomatic or uncontrolled atrial fibrillation despite treatment, or confirmed ventricular tachycardia, or presence of left bundle branch block.
 - b. Participants with a known history of congenital long QT syndrome or a first degree relative with this condition.
 - c. Clinically significant bradycardia, sick sinus syndrome, complete atrioventricular block, congestive heart failure, polymorphic ventricular tachycardia, clinically relevant hypocalcemia, hypokalemia or hypomagnesemia.
2. History of epilepsy or seizures within the last 5 years.
3. Serious medical illness includes, but not limited to, uncontrolled hypertension; respiratory disease, including severe forms of asthma; severe hepatic disease (confirmed Hepatitis B virus [HBV], Hepatitis C virus [HCV]; confirmed human immunodeficiency

⁸ If there is evidence of a prolonged QTcF interval at screening from the initial (single) administration, then the ECG will be repeated twice, and the mean of the 3 screening administrations will be used to determine whether or not the participant is suitable for inclusion in the study.

virus [HIV]); renal disease; acquired immune deficiency syndrome; and unstable psychiatric or other neurologic disorders) and metastatic cancer. For serious kidney and liver and liver illnesses see also exclusion criterion 12 (laboratory test abnormalities).

4. Known intracranial neoplasms, vascular malformations, history of cerebrovascular accident, or intracranial hemorrhage.
5. Female participants who are pregnant, planning to become pregnant or breastfeeding.

Prior/Concomitant Prohibited Therapy

6. Medications that prolong QT interval, taken within 4 weeks of the Baseline visit (note, Amiodarone is not allowed within 6 weeks of the Baseline visit) or at any timepoint during the study, including non-allowed antipsychotic medications, tricyclic antidepressants, and/or Class I antiarrhythmics as listed in Appendix 7 (Section 10.7).
7. Use of pridopidine within 12 months before the Baseline visit.

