6.7.2. Prohibited Medication

Medications specifically prohibited in the exclusion criteria are not allowed during the study. If there is a clinical indication for any medication specifically prohibited during the study, discontinuation from the investigational product may be required. The Investigator should discuss any questions regarding this with the study Medical Monitor (or designee), prior, if possible, to the administration of prohibited medications and treatments. The final decision on any supportive therapy rests with the Investigator and/or the participant's primary physician. However, the decision to continue the participant on investigational product requires the mutual agreement of the Investigator and the study Medical Monitor (or designee).

Please refer to Appendix 7, Section 10.7 for a summary of prohibited medications and substitution alternatives (note, the list of medications in Appendix 7 is not exhaustive). Any investigational agent, other than study drug, is also prohibited.

Caution should be exercised with medications that are mainly eliminated via the CYP2D6 -dependent pathway.

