10.6. Appendix 6: Permitted Medications

Note: The list of medications below is not exhaustive; please contact the study Medical Monitor (or designee) for any questions.

Medication Class	Permitted Medications	Comments
Antipsychotic	Olanzapine, fluphenazine, clorzapine, quetiapine, thiothixene, acetophenazine, trifluopromazine, loxapine, tiapride, chlorprothixene, bromperidol, tiapride and amilsupride. Aripiprazole, risperidone and perphenazine	Permitted, at no more than usual recommended doses in the approved labeling. If, according to Investigator judgment, a change of usage or dosage of antipsychotic medication is required during the study, this should be recorded in the eCRF and discussed with the study Medical Monitor (or designee).
Antidepressants	SSRIs/SNRIs including fluvoxamine*, venlafaxine, paroxetine, duloxetine, sertraline, as well as omipramol (opipramol), moclobemide, tranylcypromine, buspirone, bupropion#, reboxetine and dibenzepin	*Fluvoxamine is permitted, at no more than usual recommended doses in the approved labeling. #Bupropion dose should not exceed total daily dose of 450 mg where the daily dose is administered 3 times daily (with each single dose not to exceed 150 mg, and the rate of incrementation of dose is very gradual) (Wellbutrin® , 2017).
Antiarrhythmic	Mexiletine and tocainide	Permitted, at no more than usual recommended doses in the approved labeling.
Management of Chorea	Tetrabenazine and deutetrabenazine	Permitted, at no more than usual recommended doses in the approved labeling.
Antiviral	COVID-19 Vaccines	Vaccination (including boosters) should preferably not occur within 1 week of a study visit to ensure possible side effects do not affect the assessments

Prilenia Therapeutics

Study drug: Pridopidine
Protocol Number: PL101-HD301

Medication Class	Permitted Medications	Comments
Other	Baclofen, bupropion*, ciprofloxacin, cyclosporine, isoniazid, lindane, methylphenidate, metronidazole, penicillins, theophylline, amantadine, morphine, buprenorphine, diphenoxylate, alfentanil, fentanyl, remifentanil, meptazinol and pethidine	Only if no PK interactions are expected. *See comment above for bupropion

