10.7. Appendix 7: Prohibited Medications and Substitution Alternatives

Note: The list of medications below is not exhaustive. Prohibited medications may include different salts, esters, ethers, isomers, complexes, or derivatives of the medications listed below. In addition, there may be medications which have the potential to prolong the QT interval which are not currently on the list and are not a derivative of a listed medication. In such instances, a decision to exclude such a medication will be taken following a discussion with the study Medical Monitor (or designee) who will provide the final decision as to whether to allow the medication.

Medication Class	Excluded Medications Within 4 Weeks of the Baseline Visit (unless otherwise noted)	Substitution Alternatives (dosing of alternative medications must have been stable for at least 4 weeks before the Baseline visit and must be kept constant during the study)
Antipsychotics	Haloperidol, mesoridazine, thioridazine, pimozide, chlorpromazine, sulpiride and levomepromazine	Olanzapine, fluphenazine, clozapine, quetiapine, thiothixene, acetophenazine, trifluoperazine, loxapine, tiapride, chlorprothixene, bromperidol, tiapride and amilsupride. Aripiprazole, risperidone, and perphenazine are permitted, at no more than usual recommended doses in the approved labelling. If, according to Investigator judgment, a change of usage or dosage of antipsychotic medication is required during the study, this should be recorded in the eCRF and discussed with the study Medical Monitor (or designee).
Antidepressants	Citalopram >20 mg/day, escitalopram >10 mg/day and fluoxetine	Allowed and carefully monitored: amitriptyline, nortriptyline, imipramine, desipramine, doxepin, clomipramine, protriptyline, and amoxapine, the serotonin – norepinephrine reuptake inhibitors, and trazodone (allowed up to 100 mg/day). SSRIs/SNRIs including venlafaxine, paroxetine, duloxetine, sertraline, as well as omipramol (opipramol),

Medication Class	Excluded Medications Within 4 Weeks of the Baseline Visit (unless otherwise noted)	Substitution Alternatives (dosing of alternative medications must have been stable for at least 4 weeks before the Baseline visit and must be kept constant during the study)

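### Exclusion criterion 6 bans tricyclic antidepressants and points to Appendix 7, but Appendix 7 excludes none and lists eight such drugs as allowed

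*Protocol*

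**What the plan says.** Four parts of the protocol bear on whether a participant may take a tricyclic antidepressant.

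- **Section 5.3, criterion 6** excludes QT-prolonging medication taken in the 4 weeks before Baseline or at any time on study, "including non-allowed antipsychotic medications, tricyclic antidepressants, and/or Class I antiarrhythmics as listed in Appendix 7 (Section 10.7").
- **Synopsis (Section 1.1), criterion 8** is the same rule, "including non-allowed antipsychotic medications, tricyclic antidepressants, and/or Class I antiarrhythmics", but does not mention Appendix 7.
- **Section 6.7.2** extends the exclusion criteria into treatment: "Medications specifically prohibited in the exclusion criteria are not allowed during the study". It adds that a clinical need for such a drug may mean stopping study drug, and refers to Appendix 7 for the summary list.
- **Appendix 7 (Section 10.7)** has one row for antidepressants. The excluded column reads "Citalopram >20 mg/day, escitalopram >10 mg/day and fluoxetine". The alternatives column reads "Allowed and carefully monitored: amitriptyline, nortriptyline, imipramine, desipramine, doxepin, clomipramine, protriptyline, and amoxapine", and goes on to other antidepressants.

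Appendix 6 (Section 10.6), the permitted list, is stated to be non-exhaustive. Its antidepressant entry begins "SSRIs/SNRIs including fluvoxamine*, venlafaxine, paroxetine, duloxetine, sertraline, as well as omipramol (opipramol") and names none of the eight drugs.

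**The concern.** The criterion names a class as prohibited and sends the reader to a list. That list prohibits no member of the class and permits eight drugs by name. A site that reads the criterion or the synopsis finds a ban; a site that follows the reference to Appendix 7 finds permission.

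QT prolongation is a known risk of the study drug according to Section 2.3.1, and criterion 6 is one of the protocol's controls on it. Three things depend on the answer:

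- **On-study handling.** Under Section 6.7.2 the ban can lead to discontinuation of study drug; the permission cannot.
- **Deviation coding.** SAP Section 6.6 has a category for participants given an excluded concomitant treatment. The same prescription falls inside or outside it depending on which text is used.
- **OLE entry.** Section 5.2, criterion 1, requires completion without important deviations that affect the efficacy and safety assessments. A deviation coded as important could therefore bear on entry.

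**Working it through.** No formula applies. The check sets the texts side by side and counts list entries.

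| Source | Status of tricyclic antidepressants |
|---|---|
| Section 5.3, criterion 6 | Prohibited as a class, with Appendix 7 cited |
| Synopsis, criterion 8 | Prohibited as a class, with no appendix cited |
| Section 6.7.2 | Whatever the exclusion criteria prohibit is also prohibited on study |
| Appendix 7, excluded antidepressants | 3 entries, 0 tricyclics |
| Appendix 7, other excluded rows (antipsychotics, antiarrhythmics, other) | 0 tricyclic antidepressants |
| Appendix 7, alternatives for antidepressants | 8 named drugs allowed |
| Appendix 6, antidepressants | 0 of those 8 named |

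Four ways of removing the conflict were tried.

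1. **Read the qualifier about non-allowed drugs, and the reference to Appendix 7, as governing all three classes in criterion 6.** The tricyclic part then covers no listed drug. The other two classes do have excluded drugs in Appendix 7, so the three parts do not work alike. Synopsis criterion 8 has no reference to Appendix 7 and still reads as a class ban.

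2. **Leave it to the Medical Monitor.** In Appendix 7 that discretion is for "medications which have the potential to prolong the QT interval which are not currently on the list". These eight are on the list. Section 6.7.2 gives the Medical Monitor a say in whether a participant continues study drug, but does not settle whether a given drug is prohibited.

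3. **Leave it to eligibility review.** Section 5.1 requires the Randomization Authorization Flow reviewer to find each participant eligible. Section 5 does not permit waivers of the enrollment criteria. If criterion 6 is a class ban, the reviewer may not waive it; if it is not, no waiver is needed. The reviewer has the same two texts as the site.

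4. **Use Appendix 6.** Being non-exhaustive and silent on the eight, it neither permits nor prohibits them.

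The Schedule of Activities does not help either. Its antidepressant inquiry is general: "This information will be collected as part of the concomitant medication inquiry" (Section 1.3.1, footnote t). The ECG footnotes (m to q) concern eligibility, single or triplicate recording, timing relative to dose, and OLE entry. None attaches an assessment to these eight drugs.

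**The case against.** The best defence is that criterion 6 names classes and Appendix 7 sets status drug by drug. Antiarrhythmics offer a parallel: Class I agents are named as a class, yet Appendices 6 and 7 permit mexiletine and tocainide, which general classification places in Class I. Because Appendix 7 is not exhaustive, an unlisted tricyclic would still fall under criterion 6 and go to the Medical Monitor. On this view the stray wording is a drafting residue. The reading is possible, but the parallel is incomplete: the antiarrhythmic row has listed exclusions and the tricyclic part has none. It also leaves the synopsis uncorrected.

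Several narrower points stand in whole or part:

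- The documents do not label the eight drugs as tricyclics; that is general drug classification. Amoxapine is sometimes classed separately, leaving seven. Dibenzepin, permitted in both appendices, could be counted as a further one. The safe statement is eight named drugs, and the contradiction survives either way.
- Absence from a non-exhaustive Appendix 6 is not itself a contradiction.
- Every randomized participant passed eligibility review, so the enrollment risk is mainly that a site did not put a candidate forward.
- All participants have scheduled ECGs and are subject to the QT rules in Section 7.1.1. The undefined reference to careful monitoring in Appendix 7 is therefore missing detail, and the conclusion does not rest on it.
- What makes a deviation important is set in the Protocol Deviation Management Plan, which was not available. OLE criterion 1 also requires an effect on assessments, and with SAP version 3.0 dated 28 March 2023 many OLE entry decisions had probably been made.

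**Conclusion.** The concern holds. The protocol gives two incompatible answers on the same drugs, and neither the appendices nor the review steps choose between them. This is a conflict within a safety rule for a study drug with a known QT risk.

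Its size in the text is eight named drugs allowed against none excluded, under a criterion that bans the class. Its size in participants cannot be stated, because the documents do not say how many took one of these drugs. The SAP version history records 499 randomized participants, so Main Study screening is past. What can still be affected is deviation coding, use during the study and the OLE, and any OLE entry decision that turned on such a deviation.

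No effect is claimed on the primary analysis, on per-protocol membership (SAP Sections 4.1.3 and 4.1.4 tie exclusion to an impact on the TFC assessment) or on the randomized QTcF comparison. The conclusion assumes only that at least some of the eight drugs belong to the class named in criterion 6.

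**What to change.** Reconcile synopsis criterion 8, Section 5.3 criterion 6, Section 6.7.2 and Appendices 6 and 7 so that each of the eight named drugs has one status, stated in the same words wherever it appears. Which status applies is a clinical decision for the sponsor. While the row is being edited, either say what the reference to careful monitoring means or delete it.

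Then code excluded-medication deviations under SAP Section 6.6, and apply OLE criterion 1, from the reconciled list.

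The cost is protocol wording, a clarification letter to sites, and a check of deviation coding for participants who took one of the eight drugs. No new participants are needed. Section 4.5 says the sponsor intends a substantial amendment to extend the OLE, which could carry the correction.

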5.4. Screen Failures

Screen failures are defined as participants who consent to participate in the clinical study but are not subsequently randomly assigned to study drug. A minimal set of screen failure information is required to ensure transparent reporting of screen failure participants to meet the Consolidated Standards of Reporting Trials publishing requirements and to respond to queries from regulatory authorities. Minimal information includes demography, screen failure details, eligibility criteria not met, and any serious adverse event (SAE).

Potential candidates who do not meet the criteria for participation in this study (screen failure) may be rescreened only once.

Screening assessments may be repeated during the screening period if approved and at the discretion of the study Medical Monitor (or designee). After the screening period, all screening assessments must be repeated except for Cytosine Adenine Guanine (CAG) repeat (providing the results are available from a prior screening period).

6. STUDY DRUG

The study drug is defined as investigational intervention(s) and intended to be administered to a study participant according to the study protocol.

6.1. Study Drug(s) Administered

ARM Name	Active	Control
Study Part	Main Study and OLE	Main Study only
Study Drug Name (INN)	Pridopidine	Placebo
Type	Drug (small molecule)	-
Dose Formulation	Hard gelatin capsules	Hard gelatin capsules
Unit Dose Strength(s)	45 mg	NA
Dosage Level(s)		
Titration period	45 mg capsule QD (morning dose) for 2 weeks	Placebo capsule QD (morning dose) for 2 weeks
Main full-dose Treatment period	45 mg capsule bid (1 capsule in the morning and 1 capsule in the afternoon, 7 to 10 hours after morning dose); total daily dose of 90 mg	Placebo capsule bid (1 capsule in the morning and 1 capsule in the afternoon, 7 to 10 hours after morning dose)
Route of Administration	Oral	Oral
Use	Experimental	Placebo-comparator
Sourcing	Pridopidine drug product, manufactured by Teva Pharmaceutical Industries, Ltd or by Apotek Production & Laboratories AB (APL) or Patheon, by Thermo Fisher Scientific and provided centrally by the Sponsor or subsidiary, or designee	Placebo, manufactured by Teva Pharmaceutical Industries, Ltd or by Apotek Production & Laboratories AB (APL) and provided centrally by the Sponsor or subsidiary, or designee
Packaging and Labeling	Study drug will be provided in high-density polyethylene bottle with a child-resistant cap, labeled as required per country requirement. The secondary packaging and labeling of the study drug will be performed by Fisher Clinical Services. All packaging and labeling operations for the study drug will be performed according to current Good Manufacturing Practice for Medicinal Products and the relevant regulatory requirements.	
Prior Code Name	PL101 (formerly TV7820, ACR16 and ASP2314)	-

